8.2.1.1.2. Definition of Serious Adverse Event

An AE is considered serious if, in the view of either investigator or sponsor, it results in any of the following outcomes:

- Death,
- A life-threatening AE,
(An AE is considered “life-threatening” if, in the view of either the investigator or sponsor, its occurrence places the subject at immediate risk of death. It does not include an AE that, had it occurred in a more severe form, might have caused death. The determination of whether an AE is life-threatening can be based on the opinion of either the investigator or sponsor. Thus, if either believes that it meets the definition of life-threatening, it must be considered life-threatening for reporting purposes.)
- Inpatient hospitalization or prolongation of existing hospitalization,
- A persistent or significant incapacity or substantial disruption of the ability to conduct normal life functions, or
- A congenital anomaly/birth defect.
- Important medical events that may not result in death, be life-threatening, or require hospitalization may be considered serious when, based upon appropriate medical judgment, they may jeopardize the patient or subject and may require medical or surgical intervention to prevent one of the outcomes listed in this definition. Examples of such medical events include allergic bronchospasm requiring intensive treatment in an emergency room or at home, blood dyscrasias or convulsions that do not result in inpatient hospitalization, or the development of drug dependency or drug abuse.

This definition of an SAE permits either the sponsor or the investigator to decide if an event is serious. Because SAEs are critically important for the identification of significant safety problems, FDA believes taking into account both the investigator’s and the sponsor’s assessment is important. For example, the investigator’s perspective may be informed by having actually observed the event, and the sponsor is likely to have broader knowledge of the drug and its effects to inform its evaluation of the significance of the event. If either the sponsor or investigator believes that the event is serious, the event must be considered serious and evaluated by the sponsor for possible expedited reporting.

8.2.1.1.3. Time Period and Frequency for Collecting Adverse Event and Serious Adverse Event Information

Collection of AEs and SAEs will begin at the time a subject signs informed consent and continues until the follow-up visit. SAEs that are spontaneously reported by the subject or subject representative or discovered by the investigator or designee after the follow-up visit and up to 30 days after the last dose of investigational product must be collected and reported.

All SAEs will be recorded and reported to Worldwide Clinical Trials or Axovant Sciences within 24 hours of the investigator becoming aware of the SAE according to Section 8.2.1.1.7.

Investigators are not obligated to actively seek AEs or SAEs in former study subjects. However, if the investigator learns of any SAE, including a death, at any time after a subject has been discharged from the study, and he/she considers the event reasonably related to the investigational product or study participation, the investigator must promptly notify the sponsor or sponsor representative.

8.2.1.1.4. Assessment of Adverse Events

The severity of each AE will be assessed by the investigator, or designee approved and documented for this study, as mild, moderate, or severe based on the below definitions:

- Mild: Event that is usually transient and may require only minimal treatment or therapeutic intervention. The event does not generally interfere with usual activities of daily living.
- Moderate: Event that is usually alleviated with additional specific therapeutic intervention. The event interferes with usual activities of daily living, causing discomfort, but poses no significant or permanent risk of harm to the subject.
- Severe: Event that interrupts usual activities of daily living or significantly affects clinical status, or may require intensive therapeutic intervention.

Note that severity is not the same as “seriousness,” which is defined in Section [8.2.1.1.2](#).

Outcome will be assessed using the following categories: recovered/resolved, not recovered/not resolved, recovered/resolved with sequelae, fatal, or unknown.

Causality with respect to investigational product will be assessed as follows:

- Certain:
 - An event or laboratory test abnormality, with plausible time relationship to drug intake
 - Cannot be explained by disease or other drugs
 - Response to withdrawal plausible (pharmacologically, pathologically)
 - Event definitive pharmacologically or phenomenologically (ie, an objective and specific medical disorder or a recognized pharmacological phenomenon)
 - Rechallenge satisfactory, if necessary
- Probable:

- An event or laboratory test abnormality, with reasonable time relationship to drug intake
- Unlikely to be attributed to disease or other drugs
- Response to withdrawal clinically reasonable
- Rechallenge not required
- Possible:
 - An event or laboratory test abnormality, with reasonable time relationship to drug intake
 - Could also be explained by disease or other drugs
 - Information on drug withdrawal may be lacking or unclear
- Unlikely:
 - An event or laboratory test abnormality, with a time to drug intake that makes a relationship improbable (but not impossible)
 - Disease or other drugs provide plausible explanations
- Not Related:
 - An event or laboratory test abnormality, with a time to drug intake that makes a relationship impossible
 - Disease or other drugs provide definitive explanations

8.2.1.1.5. Method of Detecting Adverse Events and Serious Adverse Events

Care will be taken not to introduce bias when detecting AEs and/or SAEs. Open-ended and non-leading verbal questioning is the preferred method to inquire about AE occurrence. Appropriate questions include:

- “How are you feeling?”
- “Have you had any (other) medical problems since your last visit/contact?”
- “Have you taken any new medicines, other than those provided in this study, since your last visit/contact?”

8.2.1.1.6. Follow-up of Adverse Events and Serious Adverse Events

After the initial AE/SAE report, the investigator is required to proactively follow each subject at subsequent visits/contacts. All AEs and SAEs will be followed until resolution, until the condition stabilizes, until the event is otherwise explained, or until the subject is lost to follow-up (according to Section 6.6.2).

8.2.1.1.7. Reporting of Serious Adverse Events

All SAEs and deaths, regardless of relationship to the study procedures or investigational product, must be reported in English to the study sponsor or sponsor's representatives within 24 hours of the investigators first knowledge of the event through data entry in the SAE eCRF via the electronic data capture (EDC) system. In the event that the EDC system is unavailable, the paper SAE Report form should be used and emailed to Worldwide Clinical Trials Pharmacovigilance (WCT PV) at the following address:

[contact]

In the event that email reporting is not available, site personnel should fax the SAE report to:

[contact]

If notification is made via email or fax, site personnel must then enter the SAE information into the EDC system as soon as the system becomes available.

For the initial SAE notification report, the investigator must provide, at minimum, basic information such as the protocol number, subject's date of birth, subject identification number, period of investigational product intake, event term, nature of the event, the seriousness criteria, and the investigator's attribution regarding relatedness to investigational product. The initial SAE report should include all pertinent known information about the SAE and the affected subject. In addition, the investigator should provide a narrative to describe the course of events including any treatments or relevant procedures. If requested by WCT PV, any missing or additional relevant information concerning the SAE should be entered into the EDC or emailed/faxed to WCT PV.

Follow-up SAE reports may describe the evolution of the reported event and any new assessment of outcome and/or relationship to investigational product. Full supporting documentation should be solicited by the investigative site even if the SAE occurred at another institution. Such documentation may include copies of relevant medical/hospital records, pathology, or autopsy reports.

8.2.1.1.8. Regulatory Reporting Requirements for Serious Adverse Events

Prompt notification by the investigator to the sponsor or sponsor representative of all SAEs and non-serious AEs occurring during a clinical trial is essential so that legal obligations and ethical responsibilities towards the safety of subjects and the safety of a product under clinical investigation are met.

Axovant Sciences has a legal responsibility to notify both the local regulatory authority and other regulatory agencies about the safety of a product under clinical investigation. Axovant Sciences will comply with country-specific regulatory requirements relating to safety reporting to the regulatory authority, Institutional Review Board (IRB)/Independent Ethics Committee (IEC) and investigators.

Investigator safety reports are prepared for suspected unexpected serious adverse reactions (those not listed in the Investigator Brochure) according to local regulatory requirements and Axovant Sciences policy and are forwarded to investigators as necessary.

An investigator who receives an investigator safety report describing an SAE(s) or other specific safety information (e.g., summary or listing of SAEs) from Axovant Sciences will file it with the Investigator Brochure and will notify the IRB/IEC, if appropriate according to local requirements.

8.2.1.2. Safety Monitoring Committee

An independent Safety Monitoring Committee (SMC) will be established by the sponsor to review accumulating study data to monitor the safety of all subjects enrolled in RVT-101-3002 on an ongoing basis. Members of the committee will include clinicians and a biostatistician who are experienced in the conduct and monitoring of clinical studies. No Axovant Sciences employee or investigator involved in the study will be a member of the SMC or participate in closed SMC sessions. However, representatives from Axovant Sciences may attend open meeting sessions and will be available to provide additional information to the SMC as requested.

The SMC will evaluate potential safety and tolerability issues during periodic scheduled reviews of the safety data accrued during the conduct of the study. The content and format of the safety data provided will be in agreement with requests by the SMC members. Ad hoc SMC meetings may be held as necessary.

After reviewing the interim safety data, the SMC may make a recommendation to Axovant Sciences to continue the study with or without modification or to terminate the study. All SMC meetings will be properly documented in a SMC report to the sponsor.

SMC membership and responsibilities will be further outlined in the SMC Charter, which will be maintained separately from the protocol.

8.2.1.3. Physical and Neurological Examinations

Physical and neurological examinations will be performed as indicated in Table 2. Physical examinations will include, at a minimum, assessment of the cardiovascular, respiratory, gastrointestinal, and neurological systems. Neurological examinations will include assessment of gait, balance, coordination, cranial nerves and motor and sensory systems.

8.2.1.4. Vital Signs

Vital signs will be measured after the subject has been in the seated position for 5 minutes and will include systolic and diastolic blood pressures, pulse rate, respiratory rate, temperature, and body weight at each visit; height will be recorded at Screening only.

8.2.1.5. Electrocardiogram

Single 12-lead ECGs will be obtained using an ECG machine that automatically calculates the heart rate and measures PR, QRS, QT, and QTc intervals with the subject in the supine position. The investigator or designated qualified physician at the site will evaluate the Screening ECG for

any abnormalities that should exclude the subject from the study or require acute additional evaluation or intervention. They should also evaluate the ECG printouts for subsequent visits for any new abnormalities. Any abnormality should include a determination of clinical significance. A clinically significant ECG finding is one that requires additional medical evaluation or treatment.

8.2.1.6. Clinical Safety Laboratory Assessments

All protocol-required laboratory assessments, as defined in [Table 3](#), must be conducted in accordance with the central Laboratory Manual and Time and Events Schedule ([Table 2](#)). Laboratory requisition forms must be completed and samples must be clearly labelled with the subject number, protocol number, site/center number, and visit date. Details for the preparation and shipment of samples will be provided by the laboratory and are detailed in the central Laboratory Manual. Reference ranges for all safety parameters will be provided to the investigator by the laboratory responsible for the assessments.

Abnormal laboratory test results that are clinically significant should be recorded as AEs on the eCRF. Clinically significant means that the confirmed abnormal test result has an impact on subject management, including additional monitoring or diagnostic tests, or changes in treatment.

The same standard applies to additional non-protocol specified laboratory assessments that are performed at the institution's local laboratory and result in a change in subject management (ie, monitoring, diagnostic tests, or any alteration in treatment).

Refer to the central Laboratory Manual for appropriate processing and handling of samples to avoid duplicate and/or additional blood draws.

Hematology, clinical chemistry, urinalysis, and other screening laboratory parameters to be tested are listed in [Table 3](#).

Table 3. Protocol-Required Screening and Safety Laboratory Assessments

Laboratory Assessments	Parameters		
Hematology	
 • Platelet count • RBC count • Hemoglobin • Hematocrit 	
RBC Indices
 
 • MCV • MCH 	
WBC Count with Differential
 
 • Neutrophils • Lymphocytes • Monocytes • Eosinophils • Basophils
Clinical Chemistry	
 • BUN • Creatinine • Glucose 	
 • Potassium • Sodium • Calcium • Chloride • Bicarbonate 	
 • AST • ALT • Alkaline phosphatase • Total and direct bilirubin • Total protein

	
 • Albumin • GGT
Routine Urinalysis	
 • Specific gravity • pH, glucose, protein, blood, and ketones by dipstick • Microscopic examination (if blood or protein is abnormal)
Additional Tests	
 • Drug screen • Serum or urine hCG pregnancy test (for women of child-bearing potential)

Abbreviations: ALT = alanine aminotransferase; AST = aspartate aminotransferase; BUN = blood urea nitrogen; eGFR estimated glomerular filtration rate; GGT = gamma glutamyltransferase; hCG = human chorionic gonadotropin; MCH = mean corpuscular hemoglobin; MCV = mean corpuscular volume; RBC = red blood cell; WBC = white blood cell.

All laboratory tests with values that are considered clinically significantly abnormal during participation in the study or at the follow-up visit should be repeated until the values return to normal or baseline or until the value stabilizes. If such values do not return to normal within a period judged reasonable by the investigator, the etiology should be identified and the Medical Monitor notified.

8.2.1.7. Assessment of Suicidality

Subjects will be assessed for suicidality before and during the study using the Columbia Suicide Severity Rating Scale (C-SSRS). Subjects considered to be at significant risk will be excluded from the study. The C-SSRS is a brief measure which is designed to assess severity and change of suicidality by integrating both behavior and ideation. It assesses intensity of ideation (a potentially important marker of severity), specifically asking about frequency, duration, controllability, deterrents, and reasons for the ideation which was most severe during the respectively assessed timeframe. Suicidal behavior is also assessed by asking further questions to categorize the behaviors into actual, interrupted, or aborted attempts; as well as preparatory and non-suicidal self-injurious behavior. The C-SSRS will be completed by a rater who is trained and certified to administer this scale. Any change in C-SSRS score indicating the presence of suicidality should be evaluated by the investigator for clinical significance to determine continued study eligibility (Section 6.3) and appropriate clinical actions (including but not limited to a referral to a mental health professional).

Clinically meaningful suicidal ideation, suicidal behavior, and completed suicide should be recorded as AEs or SAEs.

8.2.1.8. Pregnancy

Details of all pregnancies in female subjects will be collected after the start of dosing and until 30 days after the last dose of investigational product.

Pregnancies are to be reported by the Investigator within 24 hours of the site's awareness by completing the Pregnancy Notification Form and emailing it to WCT PV at the following address:

[contact]

In the event that email reporting is not available, site personnel should fax the Pregnancy report to:

[contact]

The pregnancy must be followed up to determine outcome (including premature termination) and status of mother and child. Pregnancy complications or elective terminations for medical reasons must be reported as an AE or SAE. Spontaneous abortions, birth defects, and congenital anomalies must be reported as SAEs.

Any SAE occurring in association with a pregnancy brought to the investigator's attention after the subject has completed the study and considered by the investigator as possibly related to the investigational product must be promptly reported to the sponsor or the sponsor's representative.

The investigator must attempt to collect pregnancy information on any female partners of male study subjects who become pregnant while the subject is enrolled in the study. Pregnancy information must be reported to the sponsor or the sponsor's representative as described above. The partner will also be followed to determine the outcome of the pregnancy. Information on the status of the mother and child will be forwarded to the sponsor or the sponsor's representative. Generally, follow-up will be no longer than 6 to 8 weeks following the estimated delivery date. Any premature termination of the pregnancy will be reported.

8.2.2. Efficacy Assessments

8.2.2.1. Dependence Scale

The DS measures the amount of assistance patients with dementia require in performing daily activities. The caregiver answers questions about the dependency of the subject. The scale consists of 13 items, representing a range of severity from mild to severe levels of dependency. The score range is from 0 to 15, with higher scores indicating greater dependence.

8.2.2.2. EuroQOL-5D

The EQ-5D is a standardized measure of health status that provides a measure of health-related quality of life that is widely used in clinical trials. For this study, the EQ-5D will be a caregiver proxy assessment. The assessment will be completed by the caregiver and will assess the caregiver's impressions of how the subject would rate his/her own quality of life. The EQ-5D questionnaire consists of 2 components: the EQ-5D descriptive system and the EQ visual analogue scale. The EQ-5D descriptive system includes 5 dimensions: mobility, self-care, usual activities, pain/discomfort, and anxiety/depression. The EQ-visual analogue scale records overall health status on a 20-cm vertical line, with a score of 0 (worst health one can imagine) to 100 (best health one can imagine).

9. DATA MANAGEMENT

For this study, subject data will be entered into Axovant Sciences defined eCRFs, transmitted electronically to Axovant Sciences or designee, and combined with data provided from other sources in a validated data system.

Management of clinical data will be performed in accordance with applicable WCT standards and data cleaning procedures to ensure the integrity of the data (e.g., correcting errors and inconsistencies in the data).

AEs and medical history terms will be coded using an agreed version of the Medical Dictionary for Regulatory Activities (MedDRA), using WCT coding conventions.

Concomitant medications will be coded using the World Health Organization (WHO) Anatomical Therapeutic Chemical (ATC) classification (http://www.whooc.no/filearchive/publications/1_2013guidelines.pdf).

The eCRFs (including queries and audit trails) will be retained by Axovant Sciences, and copies will be sent to the investigator to maintain as the investigator copy.

10. STATISTICAL CONSIDERATIONS AND DATA ANALYSES

10.1. Hypotheses

Not Applicable.

10.2. Sample Size Considerations

Enrollment in this study will be based on the completion rate of the lead-in study (RVT-101-3001) and is estimated to be no more than 1150 subjects.

10.3. Data Analysis Considerations

10.3.1. Analysis Populations

One population will be considered in the statistical analysis of this study.

The Safety Population will consist of subjects who have taken at least 1 dose of investigational product. The primary population for safety analyses will be the Safety Population.

10.3.2. Interim Analysis

No interim analyses are planned.

10.4. Key Elements of Analysis Plan

All safety measures over the course of the study will be presented. Data will be listed and tabulated by the treatment groups assigned in the lead-in study and by overall; descriptive statistics will be presented for all safety parameters. Continuous data will be summarized by means, SDs, medians, maximum, minimum, and number of subjects. Categorical data will be summarized by counts and percentages. No inferential statistical analyses of safety parameters will be conducted.

10.4.1. Primary Efficacy Analyses

The efficacy analyses for DS and EQ-5D assessments will be listed and tabulated by the treatment groups assigned in the lead-in study and by overall. Details on the scoring, data imputation, and transformation will be provided in the statistical analysis plan.

10.4.2. Safety Analyses

The safety analyses will be based on the Safety Population.

The duration of RVT-101 exposure will be derived for this study. The cumulative RVT-101 exposure, including duration on RVT-101 from the lead-in study, will also be presented.

Safety and tolerability will be assessed by summarizing and analyzing AEs, discontinuations due to AEs, laboratory analytes, vital signs, ECG parameters, physical examination findings, C-SSRS scores, and concomitant medications.

10.4.2.1. Adverse Events

AEs will be considered treatment-emergent (TEAEs) if they start or worsen after first dose of the open-label treatment. If an AE begins or worsens on the first day of investigational product administration, a CRF and source data note will be provided to clarify whether it occurred prior to or after investigational product administration. TEAEs, SAEs including deaths, AEs that lead to discontinuation of investigational product, and AEs by maximum severity and relationship to investigational product will be summarized by MedDRA system organ class (SOC) and preferred term. TEAEs will also be summarized by preferred term, sorted by decreasing frequency within SOC. AEs will be summarized separately for the Open-Label Treatment Period and the Follow-up Period.

10.4.2.2. Clinical Laboratory Tests

Summaries of clinical laboratory data will be provided for subjects in the Safety Population.

Quantitative values and change from baseline in quantitative values will be summarized by planned visit for each quantitative laboratory value. Listings of all laboratory results and reference ranges will be provided. For multiple lab assessments at the same visit, the worst value will be used for the data summaries.

Laboratory values that fall outside of the reference range will be flagged as H=High or L=Low. A lab shift table may be provided to show the baseline to the worst post baseline value. Laboratory values that do not meet the laboratory abnormalities will be assigned N=normal in the shift table.

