8.1. Time and Events

The Time and Events Schedule ([Table 2](#)) displays each study assessment and procedure along with the time of occurrence. V1 of this study may be combined with the final on-treatment visit, V8, of lead-in study RVT-101-3001, or be conducted within 4 weeks of that visit. V2 will occur approximately 4 weeks after V1; V3 and V4 will each occur approximately 6 weeks after the previous visit; subsequent visits will occur approximately every 3 months thereafter. In the event of spontaneously reported tolerability problems, an unscheduled visit will be arranged to assess the subject.

All study assessments should be conducted by the investigator, and/or a suitably qualified designee approved and documented for this study. Information for each visit will be recorded in the source documents and, where appropriate, the eCRF.

V1/Screening/Baseline: The final on-treatment visit, V8, of lead-in study RVT-101-3001 may serve as V1 of this study. If V1 of this study occurs at the same time or within 7 days of V8 of the lead-in study RVT-101-3001, then the procedures conducted for V8 of the lead-in study RVT-101-3001 may serve as the procedures required for V1 of this study and need not be repeated. If V1 of this study occurs greater than 7 days after V8 of the lead-in study RVT-101-3001, then all procedures specified for V1 of this study must be repeated and cannot be combined with the procedures performed on V8 of the lead-in study RVT-101-3001. V1 of this study must occur within 4 weeks of V8 of the lead-in study.

An ICF will be signed by each subject, if he or she is able, or by the subject's legally authorized representative with subject assent before any study-specific procedures are performed. An ICF will also be signed by the caregiver before any study-specific procedures are performed. Subjects will be screened for eligibility according to study inclusion/exclusion criteria at this visit. Eligible subjects will be dispensed investigational product and will be instructed to take it once daily in the morning with or without food.

Subjects who do not qualify for the study during this visit will be considered Screen Failures, and may be rescreened (only once) after discussion with the Medical Monitor. The repeat screening visit must occur within 4 weeks of the original screening visit.

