Study Visit Number:	W0	W4	W10	W16	W28	W40	W52	W54			
Study Week:											
Study Day: relative to Baseline unless specified	0	28 ± 7	70 ± 7	112 ± 7	196 ± 7	280 ± 7	364 ± 7	14 to 19 days after last dose of IP		UNS UNS UNS	
Serum chemistry, Hematology, Urinalysis	X	X	X	X	X	X	X			X	
Serum or urine pregnancy test ^b	X						X			X	
DS	X				X		X				
EQ-5D	X				X		X				
Telephone Visit								X			

Abbreviations: AE=Adverse event; C-SSRS = Columbia Suicide Severity Rating Scale; DS= Dependence Scale; ECG = electrocardiogram; EQ-5D= EuroQOL 5 dimensions questionnaire; ET = early termination; IP=investigational product; UNS= unscheduled; V = visit; W = week.

Notes:

- The final on-treatment visit, V8, of lead-in study RVT-101-3001 may serve as V1 of this study. If V1 of this study occurs greater than 7 days after V8 of the lead-in study, then all procedures specified for V1 of this study must be repeated and cannot be combined with the procedures performed on V8 of the lead-in study. V1 of this study must occur within 4 weeks of V8 of the lead-in study.
- Unscheduled visits and/or assessments to occur at the discretion of the Investigator.
- Data for demography, standard medical history, and concomitant medications review at Screening will be rolled over from lead-in study RVT-101-3001.
- Targeted medical history will consist only of ongoing medical conditions and open AEs from the lead-in study, if any.
- Clinical prescription for donepezil will be provided by the Investigator or the treating physician.
- For ET visit only.
- Vital signs will include systolic and diastolic blood pressure, pulse rate, respiratory rate, temperature, and body weight at each visit; height will be performed at screening only.
- Pregnancy test required only for women of child-bearing potential.

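### Section 10.4.2.2 lets the worst-value rule for same-visit laboratory results choose the baseline; baseline should be one pre-specified sample chosen without regard to its value (minor, wording only)

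*Combined protocol and SAP*

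**What the plan says.** Section 10.4.2.2 of the combined protocol and SAP gives one rule for several results at one visit: "For multiple lab assessments at the same visit, the worst value will be used for the data summaries". The summaries it feeds are named in the same section: "Quantitative values and change from baseline in quantitative values will be summarized by planned visit for each quantitative laboratory value". A baseline shift display is optional: "A lab shift table may be provided to show the baseline to the worst post baseline value". Out-of-range results are marked by side: "Laboratory values that fall outside of the reference range will be flagged as H=High or L=Low". 'Worst' is not defined further, and the section does not defer the matter to a later SAP, whereas Sections 10.4.1 and 10.4.2.4 do defer details.

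Baseline is the V1 visit (Section 8.1, Table 2). When V1 falls within 7 days of the last on-treatment visit of the lead-in study (V8), the V8 procedures "may serve as the procedures required for V1 of this study and need not be repeated". Beyond 7 days the two visits may not be combined. No section says which sample is the baseline if more than one pre-dose result exists.

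**The concern.** Taking the worst of several results is a cautious convention after baseline, because it makes an abnormality more likely to show. At baseline it works the other way. A baseline picked because it was high makes later values look less changed, and a subject who would count as normal-to-high can become high-to-high. Change in laboratory assessments is part of the primary safety endpoint (Section 4), so this is the wrong direction in which to err.

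A smaller gap is that 'worst' has no direction. For analytes such as potassium or sodium (Table 3), where both high and low matter, two in-range results cannot be ranked, and the H and L flags give no order.

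**Working it through.** The plan gives no figure to reproduce: it states no laboratory SD, no within-subject correlation and no frequency of duplicates.

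**Inputs from the documents.** At most 1150 subjects (Sections 6.1 and 10.2). Laboratory samples at V1 and at six later visits, V2 to V7 (Table 2, row "Serum chemistry, Hematology, Urinalysis").

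**Assumptions, not in the documents.** Results are normal with total SD 1: X = √r·b + √(1−r)·e, with correlation r = 0.5 / 0.7 / 0.9. The upper reference limit is 1.96, 'worst' means highest, and there is no dropout. Duplicates are unrelated to their value unless stated. The share of subjects with duplicates is 5% or 20%.

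**1. How far the baseline moves.** The larger of two results exceeds their expectation by 1/√π = 0.564 within-subject SD. Multiplied by √(1−r), this is 0.399 / 0.309 / 0.178 total SD.

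**2. Shifts hidden at baseline.** Given b, a baseline result is normal with probability p = Φ((1.96 − √r·b)/√(1−r)). A post-baseline result with true rise d is normal with probability q = Φ((1.96 − d − √r·b)/√(1−r)). The chance of a shift from normal to a High worst post-baseline value is E[p(1−q⁶)] with one baseline sample and E[p²(1−q⁶)] with the worse of two. Hidden shifts per 1150 are 1150 × duplicate share × the difference. For r = 0.5 and a 20% share: 1150 × 0.20 × (0.0899 − 0.0798) = 2.3.

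| r | One sample | Worse of two | Share hidden | Hidden per 1150, 20% | Hidden per 1150, 5% |
|---|---|---|---|---|---|
| 0.5 | 8.99% | 7.98% | 11.2% | 2.3 | 0.6 |
| 0.7 | 6.41% | 5.37% | 16.2% | 2.4 | 0.6 |
| 0.9 | 3.20% | 2.43% | 23.9% | 1.8 | 0.4 |

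Shares are from unrounded values. With an assumed rise of 0.5 SD, the share hidden is 6.9 / 8.4 / 8.9%, or 3.6 / 3.4 / 2.3 shifts per 1150 at 20%, out of about 264 / 203 / 130.

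**3. Mean change from baseline.**
- Duplicates at baseline only: understated by 0.20 × 0.399 = 0.080, 0.20 × 0.309 = 0.062 and 0.20 × 0.178 = 0.036 SD. At 5% the figures are 0.020 / 0.015 / 0.009 SD.
- Duplicates equally frequent at every visit: both ends rise by the same amount. For r = 0.5, 0.080 − 0.080 = 0. The bias is zero at every correlation, with or without a true rise.
- Baseline made value-blind while later visits keep the worst value, equal duplication at 20%: mean change is overstated by 0.08 / 0.06 / 0.04 SD.

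**4. The whole rule with 20% duplicates at every visit.** Replace p by 0.8p + 0.2p² and q by 0.8q + 0.2q². Normal-to-high shifts per 1150 are then 114.6 / 79.6 / 38.3, against 103.4 / 73.7 / 36.8 with single samples throughout. With a value-blind baseline and the worst value after baseline they would be 117.1 / 82.1 / 40.1. The baseline part alone therefore still hides 2.5 / 2.5 / 1.8.

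**5. Repeats only after a High result.** The first sample is already High, so the worse of the two is High as well, and no shift is hidden relative to the first scheduled sample. In simulation the mean moves by 0.001 to 0.002 SD.

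**6. Direction.** The chance that a subject has both a High and a Low result over six visits is 0.013% at r = 0.5, that is 0.15 of 1150, and below 0.0001% at the higher correlations.

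**The case against.** The strongest reply is that the documents describe almost no route to two value-independent baseline results. Table 2 schedules one sample per visit. Section 8.2.1.6 refers sites to the laboratory manual "to avoid duplicate and/or additional blood draws" and requires repeats only for "All laboratory tests with values that are considered clinically significantly abnormal"; step 5 shows that such repeats do no harm relative to the first sample. Drug is dispensed at V1, and under Section 6.3 investigators need not wait for V8 results, so a repeat may fall after the first dose. A second set within 7 days of V8 is optional, and V8 and V1 could be kept as visits of separate studies, in which case the rule would not apply. All this stands. It limits the size but does not supply the missing baseline rule.

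A reader might also infer that the rule systematically understates mean laboratory change, or that as a whole it hides new abnormalities. The documents support neither. The rule covers every visit, and nothing shows that duplicates are more common at baseline. With equal duplication the mean bias is zero, and the net count of shifts rises (step 4).

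It may further be said that a separate SAP could settle the matter. That is possible, but no separate SAP text is supplied, and Section 10.4.2.2 states an operative rule without deferring.

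**Conclusion.** The point holds as a small correction. As worded, the rule allows baseline to be selected by its value, and for shifts this is anti-conservative relative to a single sample. The size is about 11 / 16 / 24% of normal-to-high shifts among subjects with two value-independent pre-dose results, or about 2 per analyte per 1150 at a 20% share. Both the correlations and the share are assumptions. The understatement of mean change depends on the further assumption that duplicates occur only at baseline.

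The undefined direction is mainly missing detail: it matters chiefly for two in-range values. The conclusions of the study are not threatened. No inference on safety parameters is planned (Section 10.4), all laboratory results are listed, clinically significant findings are recorded as AEs, and the shift table may not be produced.

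**What to change.** Amend Section 10.4.2.2 as one package:

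1. Define baseline as one pre-specified pre-dose sample (V1, or lead-in V8 where it serves as V1), chosen without regard to its value. State in advance which set counts when both exist.
2. Use the same value-blind rule for by-visit values and change from baseline. Items 1 and 2 belong together, because changing baseline alone would bias mean change upward wherever later visits have duplicates (step 3).
3. Keep worst-value selection only for the post-baseline side of the shift table, taken separately for the highest and the lowest value.

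The cost is wording only, with no new data. The downside is that extreme same-visit values leave the by-visit means; they remain in the listings, and in the shift table if it is produced.
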